5.6.1.1. Sensitivity to Stratification at Randomization

In order to assess the robustness of the primary analysis to stratification mistakes made at the time of randomization (i.e. the stratum recorded in IVRS/IWRS differs from the actual stratum recorded in the e-CRF), the MMRM model will be re-run replacing the IVRS/IWRS strata with the e-CRF actual strata.

5.6.1.2. Sensitivity to the Handling of Missing Data

Sensitivity analyses will be conducted to assess the robustness of primary analysis with regards to handling of missing data (3).

Visual examination:

- In order to explore the missing data pattern, post-baseline SWM strategy z-score observations during the TEAE period (in the primary safety population) will be described according to the following groups:
 - SWM strategy z-score available at week 96 (i.e. primary endpoint available),
 - SWM strategy z-score available at week 72 but missing at week 96,
 - SWM strategy z-score available at week 48 but missing from week 72,
 - SWM strategy z-score available at week 24 but missing from week 48,
 - SWM strategy z-score missing from week 24.

A graph of mean SWM strategy z-score (respectively change from baseline in SWM strategy z-score) \pm SE at baseline, and weeks 8, 12, 24, 48, 72, and week 96 will be provided by missing data pattern, for each treatment group.

- In the primary safety population, demographic and baseline characteristics will be described within the missing data pattern number 1 versus the pooled others. P-values from Chi-square test for categorical data and from asymptotic one-way ANOVA test for Wilcoxon scores (Kruskal-Wallis test) for continuous data, will be also provided, for descriptive purposes.

Multiple Imputations:

In addition to the MMRM method, the multiple imputation method (see Appendix 10.5 for more details) will be used to address missing values, in the primary safety population, followed by the testing of treatment arms using an analysis of covariance (ANCOVA) model, with the intent to evaluate the robustness of the primary analysis using a different statistical method.

Missing data from the primary safety population will be imputed 100 times to generate 100 complete data sets, using the MI SAS procedure (using Markov Chain Monte Carlo). The

percent change from baseline at week 96 will be then derived from observed and imputed SWM strategy z-score at this time point. The 100 complete data sets will be then analyzed using an ANCOVA model with treatment group and randomization strata (as per IVRS/IWRS) as fixed effects, and the baseline SWM strategy z-score as continuous covariate, and the MIANALYZE procedure will be used to generate valid statistical inferences by combining results from the 100 analyses using Rubin's formulae (4).

Pattern mixture model:

The MMRM model relies on the “missing-at-random” (MAR) assumption. Because the possibility for a not-missing-at-random (NMAR) missingness mechanism can never be excluded, sensitivity analysis to explore the impact of non-ignorable missingness on the primary neurocognitive endpoint analysis will be conducted using the pattern mixture model approach as described below (see Appendix 10.6 for more details).

In the pattern-mixture model approach, different imputation strategies will be applied to the primary neurocognitive endpoint (i.e. CANTAB cognitive domain SWM strategy z-score change from baseline to Week 96) values missing during TEAE period (i.e. within the time period from the first double-blind IMP injection up to the day of the last double-blind injection +70 days) in contrast to those missing after the TEAE period. Presented below are the reasons for considering differences in the impact of alirocumab dependent on the timing of the last study treatment administration:

- Patients who discontinued study treatment due to adjudicated neurocognitive events but are still within the TEAE period would continue to show impact from treatment similar to that observed for other patients who also had adjudicated neurocognitive events.

Note: The neurocognitive events recorded on the AE eCRF by the investigator are defined below, by any of the following programmatical procedures:

- Sponsor neurocognitive events CMQ;
- FDA neurocognitive events CMQ;
- Investigator identified NC events, as entered in the eCRF.
- Patients who discontinued study treatment due to reasons other than adjudicated neurocognitive events but are still within the TEAE period would continue to show impact from treatment similar to that observed for patients without any adjudicated neurocognitive events.
- Patients who discontinued study treatment (alirocumab or placebo) but are after the TEAE period would no longer be impacted by study treatment, and thus would have SWMS values similar to patients receiving placebo.

Missing data from the primary safety population will be imputed 100 times to generate 100 complete data sets, using the approach described above. The 100 completed datasets of

observed and imputed LDL-C data will be used for primary neurocognitive endpoint analyses.

The 100 complete datasets of observed and imputed SWMS data at week 96 will be analyzed using an ANCOVA model with treatment group and randomization strata as fixed effect, and the baseline SWMS value as continuous covariate. The MIANALYZE SAS procedure will be used to generate valid statistical inferences by combining results from the 100 analyses using Rubin's formulae (4).

5.6.1.3. Sub-group Analyses

To assess the homogeneity of the treatment effect across various subgroups, treatment-by-subgroup factor, time point-by-subgroup factor and treatment-by time point-by subgroup factor interaction terms and a subgroup factor term will be added in the primary MMRM model. LS mean difference versus placebo at week 96 will be provided, as well as the corresponding SE and 95% CI, within each subgroup. The significance level of the treatment-by-subgroup factor interaction term at week 96 will be also provided for each factor for descriptive purpose. Forest plots will be provided. In order to handle unbalances between randomization stratification factors levels, population weights will be used as for the primary analysis model.

The following subgroups of interest will be evaluated, assuming there are enough patients in each subgroup level to perform the evaluation. For the subgroup factors that are also randomization stratification factors, the IVRS strata will be used.

- The age group (<65, \geq 65) per IVRS,
- The statin use strata per IVRS (no statin, low lipophilicity of the concomitant statin, high lipophilicity of the concomitant statin),
- Gender (Female, Male)

5.6.2. Analyses of Exploratory Neurocognitive Variables

To further understand the effects of Praluent on cognitive function and support the primary neurocognitive analysis, the 3 domain endpoints (specifically PAL, RTI, and SWM between error scores) and the Global Composite score will also be evaluated for noninferiority at week 96 in the primary safety population. These 4 measures will not be evaluated for superiority. The analysis method (MMRM) and noninferiority evaluation approach (evaluation of the 95% CI for the mean treatment difference at week 96) described for the primary neurocognitive analysis will also be used for the 3 domain's z-scores change from baseline and the Global Composite score change from baseline. To support the clinical interpretation of the 3 domains, the raw score change from baseline to week 96 in the primary safety population will also be provided using the MMRM analysis method.

The 4 domain endpoint scores (including the primary neurocognitive endpoint) and the Global Composite scores will be summarized by time point (weeks 24, 48, 72, and 96) for the primary safety population as described below:

- For the 4 domain's z-score: LS mean and SE for each treatment group, obtained from the same MMRM models as used for endpoints above and including planned time points (see Section 5.6.1) and with z-score values, changes from baseline in the model as appropriate.
- For the 4 domain's raw score and the Global Composite score: LS mean and SE for each treatment group, obtained from the same MMRM models as used for endpoints above and including planned time points (see Section 5.6.1) and with raw score values, changes from baseline in the model as appropriate.

The 4 domain endpoint scores (including the primary neurocognitive endpoint) and the Global Composite scores will also be summarized descriptively by time point.

Descriptive statistics by time point for the SWM Strategy z-score and raw score will be provided for patients with 2 consecutive LDL-C < 25 mg/dL results separated by at least 21 days, or with 2 consecutive LDL-C < 15 mg/dL results separated by at least 21 days, if applicable (i.e., with enough patients).

5.6.3. Analyses of Secondary Efficacy Variables

For secondary efficacy endpoints of lipids (defined in Section 4.6.3), descriptive summaries and analyses will be performed in the ITT population (for ITT analysis) and the mITT population (for on-treatment analysis). P-values for the testing of study treatment effect will be provided for descriptive purposes only (nominal p-values).

For descriptive summaries, percent change from baseline in calculated LDL-C, Total-C, HDL-C, TG, non-HDL-C, Apo B, Apo A-1, and Lp(a) will be provided at each time point for each treatment group. All measurements, scheduled or unscheduled, will be assigned to analysis windows defined in the SAP in order to provide an assessment for these time points. Laboratory assessments other than the ones provided by the central laboratory will be excluded. The time profile of each parameter will be plotted by treatment group with the corresponding standard errors. For TG and Lp(a), summary statistics will include Q1 and Q3.

Multiple types of measurements are planned to be analyzed during the trial, specifically continuous measurements expected to have a normal distribution (eg, percent change in calculated LDL-C), continuous measurements expected to have a non-normal distribution (eg, TG), and binary measurements (eg, proportion of patients reaching LDL-C <70 mg/dL).

5.6.3.1. Continuous Endpoints Anticipated to Have a Normal Distribution

Continuous secondary efficacy variables, defined in Section 4.6.3, anticipated to have a normal distribution (ie, lipids other than TG and Lp(a)) will be analyzed in the analysis populations using the same MMRM method as described for the primary neurocognitive

endpoint (Section 4.6.1). Specifically, the model will contain fixed categorical effects of treatment group, both randomization strata, planned time points up to week 96 (specific time points are weeks 8, 12, 24, 48, 72, and 96), strata-by-time point interaction and treatment-by-time point interaction, as well as, the continuous fixed covariates of corresponding baseline value and baseline value-by-time point interaction.

5.6.3.2. Continuous Endpoints Anticipated to Have a Non-normal Distribution

Continuous secondary efficacy endpoints, defined in Section 4.6.3, anticipated to have a non-normal distribution (ie, TG and Lp(a)) will be analyzed in the analysis populations using a robust regression model (ie, ROBUSTREG SAS procedure with M-estimation option) with treatment group and randomization strata as main effect and corresponding baseline value(s) as the covariate. Missing values will be addressed using the same multiple imputation approach as described for primary neurocognitive endpoint (and using the same time points in the imputation model as described above for Section 5.6.1.2), with data log-transformed before imputation process and then back transformed to create the imputed data sets using the TRANSFORM statement of SAS MI procedure. The variables in the multiple imputation model will at least include the same variables as used in the robust regression model.

The percent change from baseline at time point of interest will be derived from observed and imputed lipid values at this time point. Multiple imputation will be followed by robust regression model to compare treatment group differences, with the endpoint of interest as the response variable using M-estimation (using SAS ROBUSTREG procedure) with treatment group, randomization strata (as per IVRS/IWRS) and corresponding baseline value(s). Combined means estimates for both treatment groups, as well as the differences of these estimates, with their corresponding SEs, 95% CIs and p-value will be provided through the SAS MIANALYZE procedure.

5.6.3.3. Binary Endpoint Variables

Binary secondary efficacy endpoints, defined in Section 4.6.3, will be analyzed in the analysis populations using stratified logistic regression (using the strata option of the SAS logistic procedure) with treatment group and randomization strata as main effect and corresponding baseline value(s) as the covariate. Missing values will be addressed using the same multiple imputation approach as described for primary neurocognitive endpoint (and using the same time points in the imputation model as described above for Section 5.6.1.2). The variables in the multiple imputation model will at least include the same variables as used in the robust regression model.

The binary endpoint at time point of interest will be derived from observed and imputed lipid values at this time point. Multiple imputation will be followed by stratified logistic regression, (with strata defined as randomized in the IVRS/IWRS) using the strata option of the SAS logistic procedure. The logistic regression procedure will be used to compare treatment group differences, with the model containing treatment group and corresponding baseline value(s) as covariate, stratified by randomization strata defined as per IVRS/IWRS. Combined estimates of odds ratio versus placebo, 95% CI, and p-value will be obtained through the SAS MIANALYZE procedure.

In the data dependent case that the logistic regression method is not applicable (eg, the response rate is zero in 1 treatment group and thus the maximum likelihood estimate may not exist), the last observation carried forward (LOCF) approach would be used for handling of missing values. Treatment effects would be compared using the stratified exact conditional logistic regression method, specifically using the strata option of the SAS logistic procedure (with strata defined as randomized in the IVRS/IWRS). The LOCF imputation method will consist of using the last value obtained up to the applicable time point window (weeks 8, 12, 24, 48, 72, and 96 as applicable) to impute the missing week value. In case the model would not converge with stratification variables, an unstratified exact logistic regression will be performed.

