2. INVESTIGATING PLAN

2.1. Study Design and Randomization

This is a randomized, double-blind, placebo-controlled trial to evaluate neurocognitive function in patients with Heterozygous familial hypercholesterolemia (heFH), or in non-familial hypercholesterolemia (non-FH) patients, at high or very high cardiovascular risk.

Patients will be randomized in a 1:1 ratio to receive either placebo or 75 mg Praluent Q2W. Randomization will be stratified by age (<65 or \geq 65) and by statin use (no statin, low lipophilicity of the concomitant statin, or high lipophilicity of the concomitant statin).

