2.2. Sample Size and Power Considerations

To demonstrate the noninferiority of the Praluent 75 mg Q2W/up-titrate 150mg Q2W dose regimen relative to placebo for the primary endpoint of mean change in Spatial Working Memory (SWM) strategy z-score from baseline to week 96, the sample size for this study is calculated to be 1085 patients per treatment group. This sample size is based on the noninferiority margin of 0.2 for the primary outcome measure. Specifically, a worsening in the SWM strategy z-score of 0 to 0.2 at the group level (small effect size) would not be considered clinically meaningful. Whereas a worsening of 0.3 to 0.5 (or greater), a small-to-medium effect size, might be considered clinically relevant, indicating increased cognitive impairment (Roiser 2015). Therefore, a noninferiority margin of 0.2 on the SWM strategy z-score change from baseline is a conservative estimate of the largest clinically meaningless mean difference between Praluent and placebo treatment groups. Additionally, the assumed mean difference between the treatment groups is 0 and the standard deviation is 1.0 (the standard deviation is obtained from the Cambridge Cognition internal normative data). To achieve 95% power using a 2-sided 95% confidence interval (CI) approach (2-sided alpha=0.05), the sample size is calculated to require 651 patients per treatment group. Assuming dropout rate of 20% in the first year and 25% in the second year, the sample size is increased to 1085 patients per treatment group.

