4.6.3. Secondary Efficacy Variable

The secondary efficacy endpoints are provided below. For those efficacy endpoints described as percent change from baseline at a given visit, the definition is: 100 multiplied (post-baseline visit measurement – baseline measurement) divided by the baseline measurement.

The baseline measurements are the last values obtained before the first dose of study treatment.

The secondary efficacy endpoint at a given visit is the measurement obtained within the analysis window of the visit and during the main efficacy period. The main efficacy period is defined as the time from the first double-blind study treatment injection up to the upper limit of the week 96 analysis window.

All secondary efficacy endpoints (scheduled or unscheduled) may be used to provide a value for the efficacy endpoint, if appropriate, according to above definition.

- The percent change in calculated LDL-C, apolipoprotein (Apo) B, non-high-density lipoprotein cholesterol (non-HDL-C), and Total-C from baseline to weeks 12, 24, 48, 72, and 96
- The percent change in lipoprotein a [Lp(a)], HDL-C, triglyceride (TG), and Apo A-1 from baseline to weeks 12, 24, 48, 72, and 96
- The proportion of patients reaching LDL-C <70 mg/dL (1.81 mmol/L) at weeks 12, 24, 48, 72 and 96
- The proportion of patients reaching LDL-C <50 mg/dL (1.29 mmol/L) at weeks 12, 24, 48, 72, and 96

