10.5. Detailed Description of the Multiple Imputation Procedure

The following is a detailed description of the multiple imputation procedure which will be used for sensitivity analysis of primary endpoint as well as the analysis of the secondary endpoints.

In general, the missing pattern is anticipated to be not monotone, a two-step approach will be used:

- Step 1: the MCMC method will be used in conjunction with the IMPUTE=MONOTONE option to create an imputed data set with a monotone missing pattern.

- Step 2: Using the monotone data set from step 1, missing data will be imputed using the regression method.

The imputation model for step 1 will include the treatment group and the values of the analyzed parameter at baseline and planned time-points up to week 96.

The imputation model for step 2 will include the same variables as in step 1 with the following additional variables:

- the randomization strata (age and statin use strata);
- age, BMI, and gender (age and BMI included as continuous variables).

Non-continuous variables included in the imputer's model (i.e., treatment group, randomization strata and gender) are not expected to be missing.

In addition, for continuous efficacy variables anticipated to have a non-normal distribution (i.e. TG and Lp(a)), data will be log-transformed before imputation process and then back-transformed to create the imputed data sets using the TRANSFORM statement of SAS MI procedure.

For variables other than those continuous efficacy variables anticipated to have a non-normal distribution (i.e. TG and Lp(a)), for each simulation leading to negative imputed value, another value will be redrawn using MINIMUM option of MI SAS procedure.

The number of imputations (100) will be informally verified by replicating sets of 100 imputations and checking whether the combined results are stable. If not stable, the number of imputations will be increased and informally checked as above, and thus continued until stable estimates are obtained.

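### LDL-C is imputed with normal errors on the raw mg/dL scale and then cut at 50 and 70 mg/dL; if LDL-C is right-skewed, the planned responder odds ratios are biased against Praluent

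*SAP*

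**What the plan says.** The SAP (4.6.3) lists two LDL-C responder endpoints at the same five visits, one at 70 mg/dL and one at 50 mg/dL: "The proportion of patients reaching LDL-C <50 mg/dL (1.29 mmol/L) at weeks 12, 24, 48, 72, and 96". SAP 5.6.3.3 fills missing LDL-C with the multiple imputation used for the primary endpoint and then dichotomises: "The binary endpoint at time point of interest will be derived from observed and imputed lipid values at this time point". The effect measure is an odds ratio from stratified logistic regression with baseline as covariate, pooled by Rubin's rules.

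SAP 10.5 gives the imputation. Step 1 uses MCMC to reach a monotone pattern. For step 2: "Using the monotone data set from step 1, missing data will be imputed using the regression method". Treatment group is a variable in both models; imputation separately by arm is not specified. The log transform is reserved for TG and Lp(a). For every other variable the safeguard is: "for each simulation leading to negative imputed value, another value will be redrawn using MINIMUM option of MI SAS procedure".

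SAP 5.6.3.1 places LDL-C among the lipids expected to be normally distributed. SAP 5.6.4 calls the lipid endpoints supportive and their p-values nominal.

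**The concern.** Normality that is adequate for a mean in an MMRM may not be adequate for a proportion below a cut-off. The regression method draws symmetric errors around each predicted value. If the true errors are right-skewed, the lower tail of the placebo draws is too heavy, and too many imputed placebo values fall below 50. In the Praluent arm, whose centre lies near the cut-offs, too few imputed values fall below them. Both errors pull the odds ratio down. Redrawing negatives does not repair this, because both cut-offs lie well above zero.

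Several features make skew credible without proving it. Entry LDL-C is truncated from below at 70 or 100 mg/dL (Protocol 4.2.1), heFH patients supply an upper tail, and the baseline categories run to 190 mg/dL and above (SAP 4.1). SAP 5.6.3.3 also has a fallback for a zero response rate in one arm, and a few imputed responders matter most when a rate is near zero. The odds ratio is the only between-group measure planned for these endpoints, and no sensitivity analysis of their imputation is specified.

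**Working it through.** **1. The plan's own figure.** The documents give no planned responder rate or odds ratio for these endpoints. The only related figure is the dropout allowance in SAP 2.2. Inputs: "This sample size is based on the noninferiority margin of 0.2 for the primary outcome measure"; "the assumed mean difference between the treatment groups is 0 and the standard deviation is 1.0"; "To achieve 95% power using a 2-sided 95% confidence interval (CI) approach (2-sided alpha=0.05"; and 1:1 allocation (SAP 2.1). The normal approximation gives n = 2 × (1.960 + 1.645)² × 1.0² / 0.2² = 649.7, so 650 per group. The noncentral t version gives 651 (power 0.9501), as stated. With 20% and then 25% dropout, 651 / (0.80 × 0.75) = 1085, also as stated. The implied share missing at week 96 is 1 − 0.60 = 40%.

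**2. Direction by hand.** The distributions are assumed. Compare a lognormal with a normal of the same mean and SD.

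- Placebo-like value, mean 100 (the non-CHD entry limit), log SD 0.25. Median = 100/exp(0.25²/2) = 96.9; SD = 100 × √(exp(0.25²) − 1) = 25.4. Below 50: lognormal Φ(−2.65) = 0.41%, normal Φ(−1.97) = 2.45%. Below 70: Φ(−1.30) = 9.7% against Φ(−1.18) = 11.9%.
- Praluent-like value, mean 57, log SD 0.5. Median 50.3; SD 30.4. Below 50: lognormal Φ(−0.01) = 49.5%, normal Φ(−0.23) = 40.9%. Removing the 3.0% negative draws gives (40.9 − 3.0)/97.0 = 39.0%, further from the lognormal value.

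**3. Simulation at trial size.** 1085 per arm, LDL-C at baseline and six visits, monotone dropout, 20 imputations, and logistic regression on treatment and baseline at week 96. Strata, age, BMI and gender were omitted because they have no effect in the simulated data. Assumed: lognormal LDL-C, base-case log SD 0.25 on placebo and 0.5 on Praluent, and a 58% reduction. Cells show placebo %, Praluent %, odds ratio.

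| Cut-off, missing | Full data | Planned method | Log scale by arm |
|---|---|---|---|
| <50, 40% | 0.56, 51.2, 255 | 1.47, 47.3, 80 | 0.57, 51.2, 263 |
| <50, 15% | 0.61, 51.8, 233 | 0.92, 50.3, 144 | 0.61, 51.8, 234 |
| <70, 40% | 6.91, 73.8, 62.4 | 7.82, 70.3, 43.7 | 6.97, 73.7, 62.0 |
| <70, 15% | 6.90, 73.9, 63.4 | 7.21, 72.6, 55.4 | 6.92, 73.9, 62.9 |

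Bias against the planned method's mean SE of the log odds ratio:

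- <50, 40% missing: ln(254.8/80.2)/0.37 = 3.1 SE.
- <50, 15% missing: ln(233.4/143.9)/0.38 = 1.3 SE.
- <70, 40% missing: ln(62.4/43.7)/0.18 = 2.0 SE.
- <70, 15% missing: ln(63.4/55.4)/0.17 = 0.8 SE.

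**4. Which arm.** Change in logit from full data to planned method, 40% missing. At <50: placebo +0.97, Praluent −0.16, so about 86% of the loss is on placebo. At <70: placebo +0.13, Praluent −0.17, so about 57% is on Praluent.

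**5. Range across assumptions (large samples).** Base-case <50 odds ratio: 237 to 168 at 10% missing, 242 to 121 at 20%, 231 to 88 at 30% and 240 to 79 at 40%. Other skewed scenarios at 40% ran from 175 to 91 (−48%) up to 1623 to 233 (−86%). At <70, 10% missing gave 65.6 to 59.8 (−9%); at 40% the losses ran from 139 to 118.5 (−15%) up to 142 to 81 (−43%). In one scenario, with equal log SDs, the placebo <70 rate fell (9.04% to 8.70%) and the whole loss came from Praluent.

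**6. Driver.** Base case <50, 40% missing, full-data odds ratio 240: raw scale with shared variance 79; raw scale by arm 67; log scale with shared variance 117. Only log scale by arm restored the value.

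**7. Near-normal errors, and the remedy.** With normal raw-scale errors the planned method gave 52 against a true 57. With symmetric errors and unequal arm SDs it gave 41 against 36; predictive mean matching by arm gave 37 and log by arm 50. In a separate lognormal run (true 269 at <50, 42 at <70), the planned method gave 173, 125 and 81 at <50 and 39, 36 and 31 at <70, for 10%, 20% and 40% missing. Matching by arm stayed at 259-296 and about 42.

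**The case against.** The strongest reply is that the condition is assumed. The documents give no LDL-C mean, SD or skew, and SAP 5.6.3.1 anticipates normality. A reader might take the redraw of negatives as a sign that the SAP expects negative LDL-C draws, or the planned summaries of LDL-C <25 and <15 mg/dL as a sign that such values are expected. Neither inference holds: the redraw is a generic guard for all variables other than TG and Lp(a), and the low-LDL-C categories are outcomes to be counted. This objection stands, and the finding is conditional on skew.

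Second, 40% missing is borrowed from the cognitive endpoint. Patients who stop drug are asked to attend all visits (Protocol 7.3.1). The ITT lipid analysis accepts values, unscheduled ones included, up to the end of a week 96 window of days 589 to 756. ITT missingness may be well below 40%. The mITT analysis, which stops 21 days after the last injection, may come closer. This stands too.

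Third, the near-zero placebo rate makes the odds ratio noisy anyway. The full-data SE at <50 is about 0.42, a 95% factor of exp(1.96 × 0.42) = 2.3 each way. The bias factor is 255/80 = 3.2 at 40% missing but only 233/144 = 1.6 at 15%. At low missingness the bias is inside the noise, though it remains systematic.

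Fourth, nothing is decided on these endpoints. LDL-C percent change by MMRM and the observed summaries do not use this imputation. That limits the importance but does not justify an avoidable bias.

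**Conclusion.** The textual point is firm: LDL-C is imputed on the raw scale with normal errors, then cut, and no other provision corrects for skew. The bias is conditional. Under assumed lognormal LDL-C the <50 odds ratio falls by about 30-40% at 10-15% missing and by about half or more at 40%; the <70 odds ratio falls by about 8-13% and 15-43%. With near-normal errors the planned method came within about 15% of the truth in either direction.

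Three stronger readings are not supported. A reader might blame the variance shared between arms, but on the raw scale imputing by arm was no better; the normal error is the main driver, and separate variances matter only once a log or matching method is used. A reader might expect false placebo responders at both cut-offs, but they are mainly a <50 problem, and at <70 much of the loss comes from the Praluent arm. A reader might fear for the trial's conclusion, but the bias runs against Praluent on supportive endpoints with nominal p-values, and the primary noninferiority result is untouched. This is a cheap improvement to make before unblinding.

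**What to change.** In SAP 5.6.3.3 and 10.5, state that for LDL-C used in the binary endpoints step 2 is run separately by treatment group with predictive mean matching (MONOTONE REGPMM). Keep the existing fallback for an arm with no responders. Matching imputes values already present in the arm's data, so step 2 cannot create week 96 placebo responders where none was observed.

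Do not offer the log transform as an equal alternative: it can be biased when LDL-C is nearly normal (50 against 36 above). At most use it, by arm, as a sensitivity analysis.

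The cost is a sentence in the SAP, slightly more programming, and a little efficiency if LDL-C is truly normal. One limit remains: step 1 still fills intermittent gaps at weeks 12 to 72 with raw-scale normal draws. Week 96 is the last planned time point, so its missing values are all left to step 2.
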